## **Study Procedures**

### **Subjects:**

Active Duty Service Members between the ages of 18-65 with a current Alcohol or Substance Use Disorder and current PTSD or trauma anxiety were recruited to be in the study.

### **Screening:**

Screening of recruited participants occurred after the subjects have been given a full description of the study procedures and have signed an IRB approved consent. Subjects were assessed for an alcohol or substance use disorder using the Mini International Neuropsychiatric Interview (MINI; Sheehan et al., 1998) or AUDIT, and PTSD using the Clinician Administered PTSD Scale (CAPS; Weathers et al., 2001) or MINI or clinician assessment for anxiety disorder NOS or DASS for anxiety/stress. The MINI will also assess for other exclusionary diagnoses where applicable (e.g., bipolar disorder, drug use disorders). The screening will include: basic vitals (heart rate, blood pressure, etc), background information including substance use history, family history of problem drinking or drug use, inclusion /exclusion criteria evaluation, as well as behavioral interviews and questionnaires listed below in data collection.

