### **Testing Procedures:**

Participants were breathalyzed and given a urine drug screen test prior to beginning the laboratory test. Participants were acclimated for approximately 60 minutes to the testing environment. Following the acclimation, baseline assessments of subjective craving and physiologic (HR, BP) measures were collected. Forty-five min prior to stress task, participants self-administered one dose of intra-nasal oxytocin (40 IUs; 5 puffs in each nostril) or saline placebo. Post-administration assessments of subjective craving and physiologic (HR, BP) measures were collected.

Trier Social Stress Test Procedure (TSST is a standardized psychological stress challenge asking subjects to give a speech and do math in front of a panel. This produces a reliable stress response across a number of subject populations. This test was adapted to be used in a group setting (TSST-G) (von Dawans, 2011). The total time for the TSST-G is 20 min.

Participants were told that they would be asked to perform a speech and mathematical calculations in front of a committee. The topic of the speech was personalized to the population. Participants were given 10 min to prepare the speech and a countdown clock placed in view of the individual. Following the speech preparation, assessments of subjective craving and physiologic (HR, BP) measures were collected.

All participants were guided to the testing room and asked to stand in a row in front of the “committee” and two conspicuous video- cameras. Participants were separated by mobile

dividing walls from other participants. Participants were instructed to deliver their speeches successively, for ~2 min each. To standardize the group experience for each subject, the first participant in each group was a confederate with a predetermined speech. After all participants had given their 2-min speech (a total of 12 min), the committee asked the subjects to serially subtract in increments of 17. Each participant received an individual starting number to avoid learning effects. If participants made a mistake, they had to restart at their starting number. Participants generally have a total of 80 s of subtraction for each participant (a total of ~8 min). Following the TSST-G, all participants were escorted back to the preparation room to obtain 4 post-task measurements over 60 minutes measuring subjective craving and physiologic (HR, BP) measures.

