## **Statistical/Data Analysis Plan**

### **Sample Size Estimation:**

It is expected that subjects treated with OT, as compared to placebo, will exhibit significantly lower levels of craving in response to the TSST. The expected effect size for these analyses (craving,  $d = 1.2$ ) is based on pilot data ( $N=16$ ) from a sample of marijuana-dependent individuals exposed to the TSST (McRae-Clark, Baker, Moran-Santa Maria, & Brady, 2013). To detect an effect size of 1.02 with a Type 1 error protection level of .05 and power ( $1-\beta$ ) of .85 (Cohen, 1988), a sample size of 20 per group would be required. Similarly, recently published data involving marijuana-dependent individuals ( $N=16$ ), suggest an effect size of .69, which would require a sample size of 33 per group ( $N=66$  total).

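### Does naming drug use disorders among the exclusionary diagnoses contradict the enrolment of people with a substance use disorder?

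*Combined protocol and SAP*

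**What the plan says.** Three statements bear on the point.

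- Subjects section: the trial took people "with a current Alcohol or Substance Use Disorder and current PTSD or trauma anxiety were recruited to be in the study".
- Screening section, on entry: "Subjects were assessed for an alcohol or substance use disorder using the Mini International Neuropsychiatric Interview", with the AUDIT given as an alternative instrument. No drug class is named.
- Screening section, on exclusion: "The MINI will also assess for other exclusionary diagnoses where applicable (e.g., bipolar disorder, drug use disorders".

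The Screening section also lists the collection of substance use history and "family history of problem drinking or drug use, inclusion /exclusion criteria evaluation". The list of criteria itself is not in the text available for this review. Under Testing Procedures, "Participants were breathalyzed and given a urine drug screen test prior to beginning the laboratory test", with no drug class and no consequence of a positive result given.

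**The concern.** One class of diagnosis appears first as a route into the trial and, a sentence later, as an example of what keeps people out. Nothing in the available text separates the drug use disorders that qualify from those that exclude.

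If the conflict were real, three things would suffer.

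- A reader could not tell whether the craving result describes alcohol use disorder alone or a mix of substances. The Data Collection section does not help, because its craving scale names no substance.
- Nobody could judge whether enrolling a person with a drug use disorder was a protocol deviation.
- The Sample Size Estimation section takes both its planning effects from cannabis users: one "from a sample of marijuana-dependent individuals exposed to the TSST", the other from "recently published data involving marijuana-dependent individuals". If drug use disorders were all excluded, those samples would resemble nobody in the trial on the substance criterion.

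**Working it through.** No figure in the plan depends on this point, so the check is one of reading. I set out the possible meanings of the exclusion sentence and what each implies for three kinds of participant, on the substance criterion only.

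| Reading of the exclusion | Alcohol disorder only | One drug disorder only | Alcohol and drug disorder |
|---|---|---|---|
| A. Every drug use disorder excludes | eligible | excluded | excluded |
| B. Drug use disorders other than the qualifying one exclude | eligible | eligible | depends on which disorders count as qualifying |
| C. Drug use disorders exclude only those who qualified on alcohol | eligible | eligible | excluded |
| D. No drug use disorder excludes | eligible | eligible | eligible |

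**Step 1: is reading A tenable?** Under A, the population statement and the entry sentence would each reduce to alcohol use disorder, and the alternative that both spell out would admit no one. The Subjects section also reports, in the past tense, that this wider population was recruited. The exclusion sentence is a parenthetical example, introduced by words that set it apart from the diagnosis just discussed and limit it to cases where it applies. A reading that empties two explicit statements to give full force to a qualified example is the poorer one.

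**Step 2: what is left without A?** In B, C and D the first two columns are the same: alcohol-only and single-drug participants are eligible. Only the last column varies. Someone with several drug disorders and no alcohol disorder is similarly unsettled under B. The uncertainty is therefore about comorbid or multiple disorders.

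**Step 3: does other text settle that remainder?** It does not.

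- The urine screen on testing day has no eligibility rule attached.
- The sample-size text gives the origin of two effect sizes and does not define who may enter. If it leans either way, planning from cannabis-dependent samples fits a trial that admits drug use disorders.
- The criteria evaluation mentioned under Screening may contain the rule, but its list cannot be seen here.

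**Step 4: what would change in the trial?**

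- The sample sizes (20 per group, or 33 per group, which is 2 × 33 = 66 in total) rest on an effect size, a significance level and a power. None of these contains an eligibility rule.
- The Data Analysis section assesses group, time, their interaction and the baseline measure for change in craving. Type of substance is not a term, so no part of that analysis is defined differently under B, C or D.
- Diagnoses are established at screening, before the testing-day dose of oxytocin or placebo. A rule used there acts on both arms alike.

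**The case for a change.** The strongest reply is that a charitable reading still does not yield one rule. Readings B and C are both reasonable and can give different answers for a person with alcohol and drug disorders together, so even a sympathetic reader cannot reconstruct what screening staff did. Because the craving scale names no substance, the eligibility rule is the main guide to what the result is about. The remedy would also be cheap: a clause in the protocol and a row in a table. Nor does the argument depend on text that cannot be seen, since the two statements in tension are both present.

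Most of the facts here are right. The rule for comorbid disorders is not in the available text, and a reader of the results will want to know the mix of substances. This shows a detail left unwritten. It does not show a design that would mislead if followed. The remedy amounts to writing down whichever rule was used, without preferring one, and it leaves sample size, procedures and the primary analysis alone. The descriptive need can be met within the plan: screening records substance use history, and the Data Analysis section already provides for a descriptive summary of clinical characteristics, where a breakdown by qualifying substance and arm naturally belongs.

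The sample-size argument does not stand as part of this point. Whether cannabis-dependent samples are a good basis for planning this trial is a separate question, and it says nothing about how the eligibility sentence should be read.

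**Conclusion.** The concern does not hold as a contradiction. The entry and exclusion statements can be read together, and on every reading that gives the entry criterion its full meaning, a person with a single drug use disorder is eligible. The remaining ambiguity concerns people with more than one substance disorder. It has no effect on the sample-size calculation or the specified primary analysis. It touches only how the enrolled population is described, a gap that analysts can fill when reporting by stating the rule used and tabulating participants by qualifying substance and arm.

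This rests on two assumptions: that screening applied one rule consistently and without regard to treatment, and that substance histories were recorded as the Screening section describes. It also has a limit: part of the document, including any formal criteria list, was not available, so the absence of a rule can be confirmed only for the text that was. A rule found there could only narrow the ambiguity further or require the wording to be aligned with it; the comparison of arms would stand either way.

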### **Female subjects screening:**

All female subjects were required to be non-pregnant, non-lactating, not trying to become pregnant, and not having unprotected intercourse during the course of the study. Females were tested for pregnancy at both study visits—at screening and on testing day. All females were

required to not have unprotected intercourse while enrolled in the study and will be tested for pregnancy at both study visits—at screening and on testing day.

### **Testing Procedures:**

Participants were breathalyzed and given a urine drug screen test prior to beginning the laboratory test. Participants were acclimated for approximately 60 minutes to the testing environment. Following the acclimation, baseline assessments of subjective craving and physiologic (HR, BP) measures were collected. Forty-five min prior to stress task, participants self-administered one dose of intra-nasal oxytocin (40 IUs; 5 puffs in each nostril) or saline placebo. Post-administration assessments of subjective craving and physiologic (HR, BP) measures were collected.

Trier Social Stress Test Procedure (TSST is a standardized psychological stress challenge asking subjects to give a speech and do math in front of a panel. This produces a reliable stress response across a number of subject populations. This test was adapted to be used in a group setting (TSST-G) (von Dawans, 2011). The total time for the TSST-G is 20 min.

Participants were told that they would be asked to perform a speech and mathematical calculations in front of a committee. The topic of the speech was personalized to the population. Participants were given 10 min to prepare the speech and a countdown clock placed in view of the individual. Following the speech preparation, assessments of subjective craving and physiologic (HR, BP) measures were collected.

All participants were guided to the testing room and asked to stand in a row in front of the “committee” and two conspicuous video- cameras. Participants were separated by mobile

dividing walls from other participants. Participants were instructed to deliver their speeches successively, for ~2 min each. To standardize the group experience for each subject, the first participant in each group was a confederate with a predetermined speech. After all participants had given their 2-min speech (a total of 12 min), the committee asked the subjects to serially subtract in increments of 17. Each participant received an individual starting number to avoid learning effects. If participants made a mistake, they had to restart at their starting number. Participants generally have a total of 80 s of subtraction for each participant (a total of ~8 min). Following the TSST-G, all participants were escorted back to the preparation room to obtain 4 post-task measurements over 60 minutes measuring subjective craving and physiologic (HR, BP) measures.

### **Debriefing:**

After the post-task assessments, participants were debriefed about the nature of the experiment. Study staff disclosed to participants that the purpose of the task to create stress and the results are not a reflection of the participant's abilities. They were informed that there was no voice, video, or behavioral recording or analysis performed based on the task, and their performance would not affect their treatment program or standing. Participants will be asked to not disclose this information to other potential participants who may not have yet participated in the study. In our experience, most cravings return to baseline (i.e., < 5) within 15 min following the stressor. Clinical staff will be notified if in the event that the craving post-test rating is significantly elevated (i.e., > 5 on the 0-10 scale. Participants will also be provided a snack or lunch at the end of the data collection.

## **Statistical/Data Analysis Plan**

### **Sample Size Estimation:**

It is expected that subjects treated with OT, as compared to placebo, will exhibit significantly lower levels of craving in response to the TSST. The expected effect size for these analyses (craving,  $d = 1.2$ ) is based on pilot data ( $N=16$ ) from a sample of marijuana-dependent individuals exposed to the TSST (McRae-Clark, Baker, Moran-Santa Maria, & Brady, 2013). To detect an effect size of 1.02 with a Type 1 error protection level of .05 and power ( $1-\beta$ ) of .85 (Cohen, 1988), a sample size of 20 per group would be required. Similarly, recently published data involving marijuana-dependent individuals ( $N=16$ ), suggest an effect size of .69, which would require a sample size of 33 per group ( $N=66$  total).

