### **Data Analysis:**

Standard descriptive statistics will be used to summarize the demographic and clinical data. Analyses will be guided by the specific hypotheses of the study. All hypotheses will be tested at level of significance  $\alpha=0.05$ . We will also estimate the effect sizes of interest and provide 95% confidence intervals. Primary outcome measure is change in craving (visual analogue scale).

Overall statistical significance for the effects of group and time, their interaction, and the baseline measure will be assessed.

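### The 33 per group for d = .69 does not follow from the stated alpha of .05 and power of .85; two-sided, it gives about 79% power

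*Combined protocol and SAP*

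**What the plan says.** The Sample Size Estimation section holds two calculations. The first reads "To detect an effect size of 1.02 with a Type 1 error protection level of .05 and power" of .85, and arrives at 20 per group. The second, introduced by the word Similarly, says that published data in marijuana-dependent individuals "suggest an effect size of .69, which would require a sample size of 33 per group", for a total of 66. The second sentence gives no alpha, power or sidedness of its own, and .85 is the only power in the document.

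The hypothesis is directional: subjects on oxytocin "will exhibit significantly lower levels of craving in response to the TSST". No one-sided test is declared, however. The Data Analysis section sets alpha at 0.05 for all hypotheses and adds: "We will also estimate the effect sizes of interest and provide 95% confidence intervals". For the model it says: "Overall statistical significance for the effects of group and time, their interaction, and the baseline measure will be assessed". The document gives no correlation between baseline and outcome, and no dropout allowance.

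**The concern.** The wording presents the two sample sizes as results of the same calculation at two effect sizes. Required sample size grows roughly as 1/d², and going from d = 1.02 to d = .69 should more than double it. The stated sizes rise only from 20 to 33, a factor of 1.65, so at least one input must have changed without being stated.

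The d = .69 case is the more conservative of the two and the only one with a stated total, so it is the figure a reader will use to judge what the trial could detect. If its power is not .85, a null result will be read as stronger evidence against an effect of that size than it is.

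**Working it through.** **Inputs from the documents.** Alpha .05 (Sample Size Estimation and Data Analysis); power .85 (Sample Size Estimation, d = 1.02 sentence); d = 1.02 with 20 per group; d = .69 with 33 per group (N=66). Sidedness is not stated, so both readings are computed. The test is taken as an unadjusted comparison of two equal groups.

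**Formulas.** Normal approximation: n per group = 2[(z for alpha + z for power)/d]². Normal quantiles: 1.960 (two-sided .05), 1.645 (one-sided .05), 1.036 (power .85), 0.842 (power .80). Exact version: noncentral t with 2n − 2 degrees of freedom and noncentrality d√(n/2).

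**Trying to reproduce 33 at d = .69**

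- Two-sided, power .85: 2[(1.960 + 1.036)/.69]² = 37.7, so 38; noncentral t gives 38.7, so 39. Not 33.
- One-sided, power .85: 2[(1.645 + 1.036)/.69]² = 30.2, so 31; noncentral t gives 30.9, so 31. Not 33.
- Two-sided, power .80: 2[(1.960 + 0.842)/.69]² = 32.97, so 33; noncentral t gives 33.96, so 34. The normal approximation at .80 matches 33 exactly.

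**Power that 33 per group gives at d = .69.** The noncentrality is .69 × √(33/2) = 2.80, with 64 degrees of freedom.

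- Two-sided: 78.8% (normal approximation 80.0%), about 6 points below .85.
- One-sided: 87.0%.
- Smallest d with .85 power at 33 per group, two-sided: 0.75.

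**The companion figure at d = 1.02** (noncentral t)

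- Two-sided, power .85: 18.3, so 19, close to the stated 20. Power at 20 is 88.2%.
- One-sided, power .85: 14.5, so 15, well short of 20. Power at 20 is 93.6%.

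**Can one convention give both sizes?** The table shows the power targets for which each stated size is the smallest sufficient integer (noncentral t).

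| Sidedness | 20 at d = 1.02 | 33 at d = .69 |
|---|---|---|
| Two-sided .05 | 86.4–88.2% | 77.6–78.8% |
| One-sided .05 | 92.5–93.6% | 86.1–87.0% |

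The ranges do not overlap under either reading. Scaling shows the same: (1.02/.69)² = 2.19, against 33/20 = 1.65. Scaling up, 20 × 2.19 = 43.7 and 19 × 2.19 = 41.5, hence about 42 to 44 per group at d = .69. Scaling down, 33/2.19 = 15.1 per group at d = 1.02. A common proportional allowance for dropout or variance leaves the ratio unchanged and cannot reconcile the two.

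**Effect of the baseline term.** The Data Analysis section includes the baseline measure. Assume d is in post-stress SD units, so that adjustment turns it into d/√(1 − r²), with 63 degrees of freedom. Two-sided power at 33 per group is then:

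| Assumed r | Power |
|---|---|
| .2 | 80.4% |
| .3 | 82.5% |
| .4 | 85.3% |
| .5 | 89.0% |

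Power reaches .85 at r of about .39. The documents give no value of r.

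**The case against.** The strongest reply is that this is an omission and not an arithmetic error. The .85 belongs grammatically to the d = 1.02 sentence, the linking word may only introduce a second data source, and 33 is the right normal-approximation answer for two-sided .80 power. That is a plausible account of where 33 came from. It does not rescue the text: a required size needs a power target, and the only one stated gives 38–39 two-sided or 31 one-sided. If .85 was not meant to carry over, the power behind N=66 is missing.

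A second reply is that the hypothesis is directional, and at one-sided .05 both stated sizes exceed .85. This is true, and it makes the 79% conditional on the two-sided reading. The support for that reading is indirect: it comes much closer to 20 at d = 1.02 (19 against 15), and alpha of 0.05 is paired with 95% intervals. The mismatch between 20 and 33 holds under either reading.

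Third, an unadjusted t-test is not the planned analysis, which has repeated assessments and a baseline term. This also stands as a qualification: the power of the planned model cannot be computed from the documents. Adjustment at a common r would lower both required sizes, so it does not reconcile the pair.

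Finally, 42 to 44 comes from approximate scaling. Taking the power range that makes 20 the two-sided minimum, noncentral t gives 40.3 to 42.5, so 41 to 43. The difference is immaterial, as either range is far from 33.

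**Conclusion.** The concern holds and should be fixed. That 20 and 33 cannot come from one calculation is certain for a two-group comparison of means and does not depend on sidedness. The size of the power gap does depend on the reading. Two-sided and unadjusted, power at 33 per group is about 79%, so the chance of missing a true d of .69 is about 21% against the 15% implied by .85. One-sided, power is about 87% and there is no shortfall, but 33 is still not the size that .85 gives. An unstated move from .85 to .80 power is the likeliest explanation. None of this shows that 66 participants is an unreasonable number; the fault is that the power behind it cannot be recovered from the stated inputs.

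**What to change.** In Sample Size Estimation, state the sidedness, the test and the power behind 33 per group. If the test is two-sided, suitable wording is:

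> With 33 per group (N=66), two-sided alpha .05 and an unadjusted two-sample t-test, power to detect d = .69 is about 79%; power of .85 is reached for d of about 0.75 or larger. Baseline adjustment may raise this, but no correlation is assumed.

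If one-sided .05 was intended, say so and give about 87% power at 33 per group. State the same inputs for the 20 per group at d = 1.02, so that a reader can see where the two calculations differ.

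The cost is one or two sentences, with no change to design or enrolment. On the two-sided reading, the reported power becomes less favourable.
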